Potential participants will be identified by reviewing Weight Watchers on line member records using our eligibility criteria of initial BMI upon entry into the program, pounds lost in the last 4-6 months, and member opted in for communications from Weight Watchers about research studies. Weight Watchers will facilitate communication to these members using existing communication channels (email). Potentially eligible individuals will be invited to visit the Way to Health portal, an NIH-funded web-based infrastructure based at the University of Pennsylvania that is used to run behavioral economic intervention studies. Participants meeting the inclusion criteria will be randomized to one of the 2 study arms through the Way to Health platform. We will use permuted block randomization with variable block sizes. Participants are randomized in a 1:1 ratio to the intervention or control arm and randomization will be stratified by: (1) sex and (2) amount of weight lost within first 4-6 months of Weight Watchers membership (<30 lbs. versus 30+lbs), as baseline weight loss may moderate treatment effects. Prior to a participant signing the informed consent, both the participant and the study coordinator will be blinded to what their potential group assignment of the participant would be if enrolled. Once consented and enrolled, neither the participants nor the study coordinator will be blinded to condition assignment due to the nature of the interventions. However, the consent form will not elucidate the design of the two intervention arms so that participants are not aware of the comparisons being made. For scientific purposes to establish valid measures of the effects of the various kinds of incentive plans, blinding participants to the overall study design is necessary, presents no increment of risk, and doesn't violate subject rights. Once a subject has been assigned to a study arm, she will receive an automatically-generated email notification about group assignment and next steps. At the close of the study, all participants will receive a debriefing letter disclosing all study arms and informing participants of the final results of the study (using de-identified data) that will be submitted for publication to an academic journal at the completion of the analysis.

Administration of Surveys and/or Process

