To enhance retention, we will provide a total of \$100 to participants in all arms. Participant compensation will be independent of degree of weight loss and randomization group as follows: \$50 for completing an online survey at the end of month 6 and at the end of month 12. All participants will also receive a free scale (value \$179). All payments will be approved electronically from the Way to Health platform. Payment information will be sent to Wells Fargo to process and sent to participants via check. Participants will receive an automated message from the Way to health platform notifying them of compensation after completing each required survey. Participants in the financial incentive arm of the study will receive additional payments based on their adherence to daily weighing at home as outlined below in Study Procedures.

Statistical Methods

Sample size justification

We have designed the study with adequate power to detect differences in maintenance of initial weight loss. Our intervention should achieve its maximal impact in maintaining initial weight loss at the end of Phase I, when the incentive payments cease. The primary analysis will be an intent-to-treat analysis that compares the weight loss at 6 months between the lottery and control arms, using a t-test at the 0.05 level for significance. Assuming 20% missingness, a 5 kg (11 lb) SD for weight change at 6 months, and at least 5 lb more weight loss for the intervention arm compared to control at 6 months, we will have at least 90% power to detect the improvement in our primary outcome.

Analytic approach

Primary and key secondary outcomes

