The primary analysis will be an unadjusted between-arm comparison of the change in weight from baseline (randomization) to 6 months, using a t- test performed at the 0.05 significance level. The primary analysis will be done as an intent-to-treat (ITT) analysis, including each participant in the group to which she was randomized, regardless of adherence to the assigned intervention. The 6-month weight is determined as the first weight that is inside the 6-month visit window. A multiple imputation strategy based on baseline covariates (including study arm) will be used to fill in the missing data for the primary outcome. For more details see multiple imputation strategy below. A complete case analysis will be done as a sensitivity analysis. A second sensitivity, assuming weight returned to baseline (weight at time of randomization) may also be considered. We will also estimate the difference between arms at 6-month in an adjusted analysis where the change from baseline is regressed in a linear model on study arm, baseline weight, and other covariates including age, sex, race, BMI, education, income, and physical activity (total MET-minutes/week).

Analyses of the key secondary outcome, weight change between baseline and 12 months (Phase 2) will be conducted in a similar manner as the primary outcome. The 12-month weight is determined as the weight that is the first weight inside the 12-month visit window. The multiple imputation algorithm for the 12-month outcome will additionally consider the 6-month weight outcome as an additional predictor, using a chained imputation type approach.

Multiple Imputation Strategy

Missing primary outcome data, weight at 6 months, will be imputed using baseline covariates only (Imputation A); variables include age, sex, race, weight, BMI qualifying weight loss, education, income, IPAQ activity level, MET-minutes walking, the three domains of eating behaviors (cognitive restraint, uncontrolled eating, emotional eating, and two scores related to delayed gratification behavior. A supportive analysis will also be done also using post-randomization variables (Imputation B); these variables include the most recent logged weight and time since last weight, The imputation strategy for the weight at 12 months and other secondary outcomes will proceed in a similar manner. Weight at 12 months will additionally use the 6-month weight outcome, using chained imputation approach (1).

Analysis of other outcomes

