The trend over time for the frequency of at-home weight measurements will be compared between arms using a generalized estimating equation (GEE) with an autoregressive (AR-1) working correlation model; specifically the mean number of days out of 7 is modeled and compared among study arms adjusting for study week and a week-by-arm interaction. Separate models will be fit for Phases 1 and 2. A linear mixed effects model with random intercept and slope for week will also be considered. An overall average weekly frequency of weighing in will be compared between arms for Phase I and Phase II using a similar GEE approach.

Additional secondary analyses include a between-arm comparison of the percent of individuals who maintained their weight (defined as gaining no more than 1.36 kg or 3 lbs) at 6 and 12 months. We will consider whether the amount of weight gain is correlated with the average number of times per week participants weighed themselves in a cross-sectional analysis at 6 and 12 months. Comparisons will also be made of the changes in self-reported physical activity and the three domains of eating behaviors (cognitive restraint, uncontrolled eating, emotional eating) at 6 months and 12 months after initial weight loss. Descriptive analyses will be done to examine the proportion of the time people fall off the lottery escalation ladder and the number of resets to beginning for the lottery incentive arm. All secondary analyses will follow in a manner similar to the primary analysis, considering both an unadjusted and adjusted approach. Imputation models for the secondary outcomes will include as predictors the baseline value for that outcome and the other baseline covariates considered for the imputation strategy A model, as described above. For secondary outcomes with < 10% data missing data, only a single imputation strategy (imputation A) may be considered.

Exploratory Analyses

We will summarize the frequency of the self-reported weights in Phase I and Phase II and examine whether there will be a difference by arm. We will further explore intervention effects and examine whether there may be a potential interaction between the baseline delayed gratification score and treatment arm.

Study Procedures

Procedures

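### Randomization is stratified by sex and prior weight loss, but the primary t-test uses neither factor and the adjusted model does not name prior weight loss; adjusting would cost almost nothing and may gain precision.

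*Combined protocol and SAP*

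**What the plan says.** Under Method for Assigning Subjects to Groups, "randomization will be stratified by: (1) sex and (2) amount of weight lost within first 4-6 months of Weight Watchers membership", with a cut at 30 lb, permuted blocks of variable size and 1:1 allocation. The reason given for the weight-loss factor is "as baseline weight loss may moderate treatment effects".

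Under Primary and key secondary outcomes, "The primary analysis will be an unadjusted between-arm comparison of the change in weight from baseline (randomization) to 6 months", by t-test at the 0.05 level. Neither stratification factor enters that test. The same section plans a supporting linear model of weight change on study arm, baseline weight and "other covariates including age, sex, race, BMI, education, income, and physical activity (total MET-minutes/week"). Sex is there and prior weight loss is not named, although the list is open-ended.

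The Multiple Imputation Strategy does use both factors. For Imputation A, "variables include age, sex, race, weight, BMI qualifying weight loss, education, income, IPAQ activity level", with further items after these. I read the run-together words as two variables, BMI and qualifying weight loss. The information is therefore in the analysis data.

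The 12-month weight change is to be analysed like the primary outcome. Under Analysis of other outcomes, "All secondary analyses will follow in a manner similar to the primary analysis, considering both an unadjusted and adjusted approach".

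**The concern.** Stratified blocks make the arms nearly equal in sex and in prior weight loss. If those factors predict 6-month weight change, the treatment difference varies less from trial to trial than it would under simple randomization. An unadjusted t-test does not know this. It estimates its standard error from the total variance, including the part between strata. The interval is then wider than the design warrants, the test rejects less than 5% of the time under the null, and some power is lost.

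At stake is precision only. There is no bias and no inflation of type I error. The point is also separate from effect moderation, which is the plan's reason for stratifying on prior loss: a main-effect adjustment does not test moderation.

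**Working it through.** **Inputs from the documents.** 259 randomized 1:1; "Assuming 20% missingness, a 5 kg (11 lb) SD for weight change at 6 months"; a 5 lb difference; level 0.05. I take the test as two-sided, since sidedness is not stated.

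**The plan's own figure.** Observed per arm: 129.5 × 0.8 = 103.6. Standardized difference: 5/11 = 0.455. Standard error of the t-test: 11 × √(2/103.6) = 1.53 lb. Power from the noncentral t is 90.25% (90.5% by normal approximation). The stated power of 90% or more reproduces.

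**Assumed input.** The documents give no R² (the share of variance in weight change explained by the strata). I use 0 to 0.20. If all of it comes from prior loss and the two groups are equal in size (also assumed), the difference in mean weight change between them is 2 × 11 × √R².

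**Closed form, strata balanced between arms**, with SE = 1.528 lb:

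- True SD of the estimated difference: SE × √(1−R²)
- Excess width of the t-test interval: 1/√(1−R²) − 1
- Type I error of the t-test: 2 × [1 − Φ(1.96/√(1−R²))]
- Power of the t-test: Φ[(5 − 1.96 × SE)/(SE × √(1−R²))]
- Power with strata in the model: Φ[5/(SE × √(1−R²)) − 1.96]

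| R² | Implied difference between prior-loss groups (lb) | t-test interval too wide by | t-test type I error | t-test power | Adjusted power | Gain (points) |
|---|---|---|---|---|---|---|
| 0 | 0 | 0% | 5.0% | 90.5% | 90.5% | 0 |
| 0.01 | 2.2 | 0.5% | 4.9% | 90.6% | 90.8% | 0.2 |
| 0.05 | 4.9 | 3% | 4.4% | 91.1% | 91.9% | 0.8 |
| 0.10 | 7.0 | 5% | 3.9% | 91.7% | 93.2% | 1.5 |
| 0.20 | 9.8 | 12% | 2.8% | 92.9% | 95.5% | 2.7 |

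Gains are taken before rounding. Worked row for R² = 0.10: √0.90 = 0.949; adjusted SE = 1.528 × 0.949 = 1.450; adjusted power = Φ(5/1.450 − 1.96) = Φ(1.49) = 93.2%.

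**Simulation, complete cases.** N = 259, four strata, blocks of 2/4/6, each factor split 50/50, 20% missing completely at random, 8,000 trials per setting. Block sizes, splits and missingness mechanism are assumptions. For R² of 0 / 0.05 / 0.10 / 0.20, t-test type I error was 5.2 / 4.5 / 3.8 / 3.4% and the ratio of interval widths 1.00 / 1.03 / 1.05 / 1.12.

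A second complete-case simulation used unequal strata (assumed 20% men and 40% in the higher-loss group; 5,000 trials per setting). T-test power was 90.3 / 90.9 / 91.8 / 92.4% against 90.2 / 91.5 / 93.5 / 95.6% adjusted. At R² = 0.20, type I error was 3.4% for the t-test and 4.9% adjusted.

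**Simulation with multiple imputation.** Same set-up as the first, with 20 imputations (assumed), an imputation model of arm, sex, prior-loss stratum and baseline weight, and Rubin's rules. This is a reduced form of Imputation A, which lists more covariates.

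| R² | t-test power | Adjusted power | Gain (points) | t-test interval too wide by | t-test type I error |
|---|---|---|---|---|---|
| 0 | 89.4% | 89.5% | 0.1 | 0% | 5.2% |
| 0.05 | 89.9% | 90.6% | 0.7 | 2% | 4.5% |
| 0.10 | 90.9% | 92.4% | 1.5 | 4% | 4.3% |
| 0.20 | 92.6% | 94.9% | 2.3 | 10% | 3.3% |

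Monte Carlo error in the 8,000-trial runs is about 0.2 points for type I error and 0.3 for power. Imputing with the strata therefore does not remove the loss, because the test on the completed data still ignores them.

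**Baseline weight** is an ordinary covariate, not a stratification factor. If prior loss explained 15% of the variance and baseline weight a further 5% (assumed), the SE would go from 1.53 lb to 1.528 × √0.85 = 1.41 with the strata, and to 1.528 × √0.80 = 1.37 with baseline weight added. Under imputation the simulated figures were 1.51, 1.41 and 1.38 lb.

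**The case against.** The strongest reply is that nothing in the plan fails. An unadjusted primary test with an adjusted supporting analysis is a legitimate prespecified choice, the error is on the conservative side, and the power target is met. That stands, and it limits this to an efficiency point.

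The second reply is that R² may be small. The plan stratifies because prior loss might modify the effect of treatment, not because it is said to predict weight change. On equal groups, R² = 0.05 already needs a 4.9 lb difference, about the size of the target effect. With only 20% in one group it needs 11 × √0.05/0.4 = 6.1 lb. At R² = 0.01 the gain is 0.2 points. This also stands: the benefit is conditional, and 0.20 is a high upper end. It does not favour the t-test, because adjustment takes two parameters out of about 205 degrees of freedom and showed no visible power loss at R² = 0.

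Third, much is already in place: sex and baseline weight in the adjusted model, an open covariate list, and both factors in Imputation A. This is true, but none of it changes the standard error of the primary test.

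Fourth, the closed form overstates the conservatism slightly (2.8% against 3.3 to 3.4% in the simulations at R² = 0.20), and the imputation model simulated was smaller than the planned one. Both are fair. The secondary outcomes are promised an adjusted analysis too, and no figures were computed for the binary maintenance outcome or the GEE models, so the sizes here apply to weight change only.

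**Conclusion.** The concern holds. The primary test ignores both factors used to stratify randomization, and prior weight loss is the one factor the adjusted model does not name. The t-test remains valid and the stated power is correct. If the strata explain 5 to 10% of the variance in weight change, the primary interval is about 2 to 5% wider than it need be and about 0.7 to 1.5 points of power are forgone. At 20% the figures are 10 to 12% and 2.3 to 2.7 points, and at zero nothing is lost either way. These sizes rest on assumed R², stratum splits and block sizes, and on missingness completely at random in the simulations.

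In terms of recruitment, matching the adjusted interval with a t-test would take about 259 × 0.05/0.95 = 14 more participants at R² = 0.05, or 259 × 0.10/0.90 = 29 more at R² = 0.10. The change is worth making because it costs almost nothing, not because the trial is at risk.

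**What to change.** Make the primary test a linear regression of 6-month weight change on study arm, baseline weight, sex and prior weight-loss stratum (under 30 lb / 30 lb or more). Run it on the Imputation A datasets and combine by Rubin's rules at the 0.05 level. Keep the unadjusted t-test as a sensitivity analysis. Name prior weight loss in the existing adjusted model, and use the same structure for the 12-month weight change. If the t-test is kept as primary, at least add prior weight loss to the adjusted model.

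The cost is SAP wording. All three covariates are known at randomization and already listed for Imputation A, and a linear model is already planned. No new data or participants are needed. The documents do not state how far enrolment or data access had gone, so the change should be dated and made before outcomes are seen by arm.

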Our previous work examining the impact of different degrees of cost sharing on employee participation, engagement, and ongoing weight loss showed that among Weight Watchers members who had initial success in losing at least 5% of their initial body weight, the majority regained weight over the subsequent 6 months; Weight Watchers members in general were at high risk of dropping out of the program altogether perhaps due to lack of success in losing weight and keeping it off (John et al 2015). Research has shown that the frequency of self-weighing is important for both prevention of weight gain and weight loss (Wing et al NEJM 2006; 355:1563-1571; Linde JA et al Ann Behav Med 2005; 30: 210-216). This study will build on our successful efforts using incentives for weight loss to test scalable ways of increasing the frequency of self-weighing among Weight Watchers members who had initial success in losing weight. This 2- arm randomized controlled trial will compare the relative effectiveness and cost-effectiveness of (1) weekly feedback without incentives to (2) weekly escalating lottery-based incentives among patients who successfully lost at least 5 kg over 4-6 months during participation in Weight Watchers (Pre Phase). Incentives will be provided to some study participants (Arm 2) for the first 6 months (Phase I), and then participants will be followed for 6 more months to examine effects following cessation of incentives (Phase II). A total of 259 participants will be randomized into the 2 arms.

Specific Aims

Aim 1: Among participants who lose 5 kg or more of baseline weight prior to randomization, assess the effectiveness of escalating lottery rewards, relative to the control group, on maintenance of weight loss over the ensuing 6 months (Phase I).

Aim 2: Assess the degree to which weight loss is maintained in the intervention group relative to usual care during the 6 months following the cessation of the interventions (Phase II).

Objectives

Overall objectives

- 1. Among participants who lose 5 kg or more of baseline weight prior to randomization, assess the effectiveness of escalating lottery rewards, relative to the control group, on maintenance of weight loss.
- 2: Assess the degree to which weight loss is maintained in the intervention groups relative to usual care during the 6 months following the cessation of the interventions (Phase II).

Primary outcome variable

Pounds of weight lost at the end of 6 months

Secondary outcome variables

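### The planned correlation of weight gain with weigh-in frequency would, under the plan's general rule, use weights imputed without weigh-in frequency, which pulls the association toward zero

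*Combined protocol and SAP*

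**What the plan says.** All references are to the combined protocol and SAP.

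- **Analysis of other outcomes** plans the association, among the additional secondary analyses: "We will consider whether the amount of weight gain is correlated with the average number of times per week participants weighed themselves". It is cross-sectional, at 6 and at 12 months.
- The same section sets the general rule: "All secondary analyses will follow in a manner similar to the primary analysis, considering both an unadjusted and adjusted approach". On missing data it adds: "Imputation models for the secondary outcomes will include as predictors the baseline value for that outcome and the other baseline covariates", meaning those of strategy A. Where under 10% of the data for a secondary outcome are missing, strategy A alone may be used.
- **Primary and key secondary outcomes** and **Multiple Imputation Strategy** define strategy A as baseline covariates, with study arm. Supportive strategy B adds the last weight recorded and how long ago it was recorded. The 12-month model adds the 6-month weight. None of these lists names weigh-in frequency. A complete-case analysis is planned as a sensitivity analysis.
- The 6-month endpoint is the earliest weight in its visit window, and **Procedures** says that weights arrive from the internet-enabled home scale.
- **Sample size justification** gives the planning figure for missing data: "Assuming 20% missingness, a 5 kg (11 lb) SD for weight change at 6 months".

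**The concern.** An imputation model that leaves out a variable used in the analysis model assumes that the imputed values are unrelated to that variable, given the predictors that are included. Here the omitted variable is the exposure itself. Each imputed participant contributes a weight change that knows arm and baseline but not how often the person weighed in, so the estimate is diluted even if weights are missing completely at random.

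The measurement process is likely to make this worse. A weigh-in is both a unit of the exposure and a chance to record the endpoint. Rare weighers are therefore the likeliest to lack a weight in the window, and they sit at the end of the frequency scale where they have most influence on a slope. The documents do not state this link; it is inferred from how weights are collected.

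The analysis bears on the trial's rationale, that frequent self-weighing goes with keeping weight off. An estimate diluted by its imputation model could lead readers to discount a real association.

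**Working it through.** **Inputs from the documents.** N: "A total of 259 participants will be randomized into the 2 arms". Allocation: "Participants are randomized in a 1:1 ratio to the intervention or control arm". Missing: 20%. SD: 11 lb. Difference: "at least 5 lb more weight loss for the intervention arm compared to control at 6 months". Test: "using a t-test at the 0.05 level for significance", taken as two-sided because sidedness is not stated.

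**The plan's own figure.** No figure is given for the association. The primary power statement, which supplies N and the 20%, reproduces:
- Completers per arm = 259 × 0.80 / 2 = 103.6.
- Standard error = 11 × √(2/103.6) = 1.528 lb, and 5/1.528 = 3.27.
- Power ≈ Φ(3.27 − 1.96) = 90.5% (90.3% by noncentral t), against at least 90% stated.

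**Expected shrinkage when missingness is unrelated to frequency.** Observed participants keep the full association. Imputed ones keep only the part that travels through arm. With share missing *m* and share of frequency variance explained by arm *a*:

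ratio ≈ (1 − *m*) + *m* × *a*

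If the arms differ by 0.5 within-arm SD in frequency (assumed), *a* = 0.5² × 0.25 / (1 + 0.5² × 0.25) = 0.0625/1.0625 = 0.059. Then the ratio = 0.80 + 0.20 × 0.059 = 0.81, a loss of 19%. If the association is adjusted for arm, the second term drops out and the ratio is about 0.80. Adjusting for arm therefore does not cure the dilution.

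**Simulation of the correlation.** 259 participants, 400 replicates, 10 imputations, 20% missing. Assumed: true r = −0.30; baseline covariates explain 5% of outcome variance; last logged weight correlates 0.6 with the outcome; time since last weight tracks frequency. Mean estimates:

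| Missingness | Full data | A | B | A + frequency | Complete cases |
|---|---|---|---|---|---|
| Unrelated to frequency | −0.301 | −0.243 | −0.290 | −0.302 | −0.303 |
| Moderate dependence | −0.304 | −0.217 | −0.285 | −0.302 | −0.286 |
| Strong dependence | −0.300 | −0.171 | −0.267 | −0.294 | −0.250 |
| Only the rarest weighers missing | −0.301 | −0.150 | −0.259 | −0.298 | −0.235 |

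Loss is 1 − estimate/full data.
- Under A, from 1 − 0.243/0.301 = 19% to 1 − 0.150/0.301 = 50%.
- Under B, from 1 − 0.290/0.301 = 4% to 1 − 0.259/0.301 = 14%.
- Complete-case correlations fall, to −0.235 at worst, because dropping rare weighers narrows the frequency range.
- With 10% missing, A gives −0.27 to −0.20. With 30%, it gives −0.22 to −0.11.

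**Simulation of the slope.** N = 259, 600 replicates, 20% missing. Assumed: slope −1.5 lb per weigh-in day per week, residual SD 10, missingness logistic in frequency with log-odds 0, 0.5, 1 and 2 per day per week.
- Ratio of imputed to full-data slope under A: 0.83, 0.73, 0.62, 0.51.
- With frequency in the imputation model: 0.99 to 1.01.
- Complete-case slope under the same slope, residual SD and log-odds: 0.99 to 1.00.
- A separate slope simulation gave 0.81 to 0.52 under A, and 0.99 to 1.03 with frequency included.

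No calculation was made for the 12-month model. It also uses the 6-month weight, which may carry some information about frequency.

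**The case against.** **The premise is inferred.** No sentence says that imputed weights enter this correlation. It is introduced as something to be considered, is not among the twelve listed secondary outcomes, and the imputation sentence speaks of secondary outcomes. The predictor lists may also be incomplete. This stands as a limit. But the general rule covers all secondary analyses, strategy A is restricted to baseline covariates, and no separate missing-data rule is given.

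**The plan has partial safeguards.** Strategy B brings the simulated loss down to between 4% and 14%, and the allowance to use A alone does not apply at 20% missing. Complete-case analysis carries over by the same general rule and recovers the slope when missingness depends only on frequency. A reader might infer that a null result could not be interpreted at all. The documents do not support that: a null under A beside a clear complete-case slope would itself be informative. What remains is that the leading estimate is the one most diluted.

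**Arm adjustment.** A reader might also infer that the two arms are pooled with no account taken of arm. The general rule calls for unadjusted and adjusted approaches, and the primary adjusted model contains study arm, so adjustment is already provided for.

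**Magnitudes.** The true association, residual SD, missingness mechanisms and the behaviour of strategy B's predictors are all assumed. Near-perfect recovery is expected when data are generated as linear and missing at random given frequency.

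**Conclusion.** The point holds for this secondary association. Following the general rule, strategy A biases the estimate toward zero. At N = 259 and 20% missing, the loss is about 17% to 20% if missingness is unrelated to frequency and up to about 50% if it concentrates in rare weighers. The direction follows from the omission of frequency whenever a true association exists; the size depends on the assumptions above.

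It does not extend to the primary between-arm comparison, whose imputation model contains arm and whose analysis does not use frequency. It warrants a correction before analysis but does not threaten the trial's main result.

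**What to change.** In Analysis of other outcomes, state the missing-data rule for this association. Either:

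- for this analysis only, include phase-average weigh-in frequency, together with arm, in the 6- and 12-month weight imputation models; or
- make the complete-case regression of weight change on frequency the lead analysis.

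Report both in either case. Give the regression slope as well as any correlation, because the complete-case correlation shrinks when the range of frequency narrows. Leave the imputation for the primary comparison as it is.

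The cost is a short SAP addition and one extra imputation run on data already collected. There are two small drawbacks. The imputation extrapolates to rare weighers, among whom few weights are observed. The plan must also say how weeks after withdrawal count toward average frequency (as zero or as missing), which the documents do not settle.

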Basic demographic data (BMI, gender, race, education, income, household size), physical activity data (IPAQ long), and eating behavior questions (TFEQ) and 2 questions measuring delayed gratification will be collected upon enrollment. We will also collect this data, minus the demographic questions, at 6 and 12 months.

Protocol

Abstract

Obesity is the second leading cause of preventable death in the United States, (1) associated with high blood pressure (BP), type 2 diabetes, coronary heart disease, and osteoarthritis. Identifying effective strategies for treating obesity is both a clinical challenge and a public health priority. Over 70% of the U.S. population is overweight or obese, and obesity in middle age translates into higher rates of hospitalization, Medicare expenditures, disability, and mortality risk in subsequent years. While a variety of approaches are successful in achieving initial weight loss, techniques for maintenance of initial weight loss have largely been unsuccessful.

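### For the activity and eating-behavior outcomes, the unadjusted change score leads by inheritance from the primary analysis, and adjustment for the outcome's own baseline is named for only 2 of 12 comparisons

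*Combined protocol and SAP*

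**What the plan says.** Secondary outcomes 7-10 are three self-reported activity measures (total MET-minutes/week, MVPA minutes, walking minutes) and three eating-behavior domains, each at 6 and 12 months. Statistical Methods, under Analysis of other outcomes, says "Comparisons will also be made of the changes in self-reported physical activity and the three domains of eating behaviors". The same paragraph sets the general rule: "All secondary analyses will follow in a manner similar to the primary analysis, considering both an unadjusted and adjusted approach".

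The template is under Primary and key secondary outcomes. Its main analysis is an unadjusted t-test on change in weight from randomization. It then adds a linear model of change on study arm, baseline weight and "other covariates including age, sex, race, BMI, education, income, and physical activity (total MET-minutes/week". In that model baseline weight is the outcome's own baseline.

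The baseline scores will be available. The activity and eating questionnaires are given at enrollment, and Administration of Surveys and/or Process adds: "We will also collect this data, minus the demographic questions, at 6 and 12 months". The imputation models for secondary outcomes are explicitly required to include each outcome's own baseline. The analysis models carry no matching requirement.

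**The concern.** The plan leaves two things open for outcomes 7-10.

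- **Which analysis leads.** Both an unadjusted and an adjusted analysis are planned, and the plan does not rank them for these outcomes. The only ranking available is the primary's, where the unadjusted change score comes first.
- **What the adjusted model contains.** Applied as written, the covariate list gives an eating-domain model baseline weight and total MET-minutes/week, but not the baseline eating score. An analyst may well substitute the right baseline, but has to infer it.

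The change score is a reasonable lead where baseline and follow-up are very closely correlated. If questionnaire scores taken 6 or 12 months apart correlate less closely, subtracting the whole baseline adds noise and over-corrects chance imbalance between arms. The stakes are wider intervals than the collected data allow, and a choice between two analyses that could be made after the results are seen.

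**Working it through.** **1. The plan's own figure.** The only power statement concerns weight. Inputs:
- "A total of 259 participants will be randomized into the 2 arms" (Abstract)
- "Participants are randomized in a 1:1 ratio to the intervention or control arm" (Method for Assigning Subjects to Groups)
- "using a t-test at the 0.05 level for significance" (Sample size justification); sidedness is not stated, so two-sided is assumed
- "Assuming 20% missingness, a 5 kg (11 lb) SD for weight change at 6 months, and at least 5 lb more weight loss" (Sample size justification)

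Analyzed per arm: 259 × 0.8 / 2 = 103.6. SE = 11 × √(2/103.6) = 1.528 lb. Power = Φ(5/1.528 − 1.96) = Φ(1.31) = 90.5%, or 90.3% with the noncentral t. The stated figure of at least 90% reproduces. No power or precision is stated for outcomes 7-10.

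**2. Count of comparisons.** (3 activity + 3 eating) × 2 time points = 12. Own baseline is named in the adjusted model for total MET-minutes/week only: 1 × 2 = 2. It is not named for the other five measures: 5 × 2 = 10.

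**3. Direction.** Let s0 and s1 be the baseline and follow-up SDs and r their within-arm correlation. Per participant:
- Var(change) = s0² + s1² − 2·r·s0·s1
- Var(adjusted for own baseline) = s1²(1 − r²)
- Difference = s0² − 2·r·s0·s1 + r²·s1² = (s0 − r·s1)², which is never negative

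So in large samples own-baseline adjustment is never less efficient than the change score, whatever r and the variances are.

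**4. Size with equal variances.** With s0 = s1 = 1, Var(change) = 2(1 − r) and Var(adjusted) = 1 − r². Their ratio is (1 + r)/2, so the loss is (1 − r)/2. The documents give no r, so the range below is assumed. The last column uses 103.6 per arm and an effect set so that the adjusted model has 80% power.

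| r (assumed) | Information lost | Extra participants to compensate | Power of unadjusted change test |
|---|---|---|---|
| 0.3 | 35% | 54% | 62% |
| 0.5 | 25% | 33% | 68% |
| 0.7 | 15% | 18% | 73% |
| 0.8 | 10% | 11% | 76% |

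For example, at r = 0.5 the effect is (1.96 + 0.84) × √(0.75 × 2/103.6) = 0.337 SD. The change-score SE is √(1 × 2/103.6) = 0.139, so power is Φ(0.337/0.139 − 1.96) = 68%. The 103.6 borrows the 20% missingness assumed for weight; survey completion may differ, and missing values are to be imputed.

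**5. Sensitivity to equal variances.** Take r = 0.7 and s0 = 1.
- s1 = 1.2: Var(change) = 1 + 1.44 − 1.68 = 0.76; Var(adjusted) = 1.44 × 0.51 = 0.734; loss = 1 − 0.734/0.76 ≈ 3%.
- s1 = 0.8: Var(change) = 1 + 0.64 − 1.12 = 0.52; Var(adjusted) = 0.64 × 0.51 = 0.326; loss ≈ 37%.

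The size can move a long way from 15% in either direction. The sign cannot change.

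**6. Chance imbalance.** With equal variances, an observed between-arm baseline difference D moves the expected change-score estimate by (1 − r)·D, in the opposite direction to D. The own-baseline model removes this shift.

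**The case against.** The strongest reply is that the remedy is already in the plan. All secondary analyses are to have an adjusted version, and the template's adjusted model includes baseline weight, which is the outcome's own baseline. The natural reading for an eating score is to put its baseline in that place. Regressing change on arm and own baseline gives the same arm estimate and standard error as regressing the follow-up value on them. On that reading only the ranking of two planned analyses is at issue, and even that ranking is inferred.

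Much of this stands. A reader might infer that these outcomes receive no adjustment for their own baseline. The documents do not support that: total MET-minutes/week is named, and the template plausibly supplies the rest. Nor do they support saying that the plan discards a fixed share of information in all 12 comparisons, since the loss falls on the unadjusted version only and its size depends on correlations the documents do not report. Finally, the unadjusted change comparison is not biased under randomization; the shift in step 6 is conditional on a chance imbalance.

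What the reply does not remove is that own baseline is unnamed for 10 of 12 comparisons, although the authors wrote it out for the imputation models. The only ranking a reader can find also puts the less efficient analysis first.

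**Conclusion.** The point holds as a gap in specification combined with an inefficient default. The unadjusted change score leads outcomes 7-10 by inheritance from the primary analysis, and the adjusted model names own baseline for 2 of 12 comparisons.

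That own-baseline adjustment is at least as efficient rests on no assumption beyond large samples. The size does: 35% down to 10% for r from 0.3 to 0.8 needs equal variances, and at r = 0.7 a follow-up SD 1.2 times baseline cuts the loss from 15% to about 3%. These percentages should be read as illustrations for the unadjusted comparison, not as properties of the plan.

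These are secondary outcomes for which no power is claimed. The primary weight comparison and its conclusion are unaffected. The change is worth making because it costs nothing and closes an analytic choice in advance.

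**What to change.** Under Analysis of other outcomes, add wording such as:

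> For secondary outcomes 7-10, the main between-arm comparison at 6 months, and likewise at 12 months, is a linear model of the follow-up value (equivalently, of the change) on study arm and the baseline value of the same measure. The unadjusted comparison of change is supportive.

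If the fuller covariate-adjusted model is kept for these outcomes, state that it also includes the baseline value of the same measure, as the imputation models already do.

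The cost is SAP wording only. The baseline scores are collected at enrollment and already used for imputation, so no new data, visits or participants are needed. The wording should be settled before between-arm results for these outcomes are seen.
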